11.2.2 Maximum Tolerated Dose

- The MTD will be the maximum dose at which fewer than one-third of patients experience DLT (See [Section 5.6](#)) during Cycle 1 of therapy.
- In the unlikely event that two DLTs observed out of 6 evaluable patients are different classes of Adverse Effects (e.g. hepatotoxicity and myelosuppression), AND all of the following conditions are met, expansion of the cohort to 12 patients will be considered:
 - One of the DLTs does not appear to be dose and/or drug-related
 - The Adverse Effects are readily reversible
 - The study chair, DVL statistician, DVL committee chair or vice chair, and IND sponsor all agree that expansion of the cohort is acceptable
- The DLTs observed in the pharmacokinetic (PK) expansion cohort will be counted towards the total number of DLTs observed at the RP2D/MTD during the dose confirmation portion of the study. If $\geq 1/3$ of the cohort of patients at the RP2D/MTD (during the dose confirmation plus the PK expansion) experience DLT then the MTD will be exceeded.

11.3 Dose Confirmation and Determination of MTD/RP2D

The rolling six phase 1 trial design will be used for the conduct of this study.³² There is no dose escalation beyond DL1 (20 mg/m²); but the R6 logic will be used to determine the MTD/RP2D. DL1 will be defined as the RP2D if there are less than or equal to 1 patient(s) with a DLT among up to six evaluable patients. Otherwise, DL-1 will open to accrual of up to six evaluable patients. DL-1 will be defined as the MTD/RP2D if there are less than or equal to 1 patient(s) with a DLT among six evaluable patients. Otherwise, DL-1 will have exceeded the MTD and the study will close to accrual without having defined an MTD/RP2D.

In addition to determination of the RP2D/MTD, a descriptive summary of all toxicities will be reported.

11.4 Inclusion of Children, Women and Minorities

PLANNED ENROLLMENT REPORT						
Racial Categories	Ethnic Categories				Total	
	Not Hispanic or Latino		Hispanic or Latino			
	Female	Male	Female	Male		
American Indian/ Alaska Native	0	0	0	0	0	
Asian	0	0	0	0	0	
Native Hawaiian or Other Pacific Islander	0	0	0	0	0	
Black or African American	3	3	0	0	6	
White	11	17	2	2	32	
More Than One Race	0	0	0	0	0	
Total	14	20	2	2	38	

The study is open to all participants regardless of gender or ethnicity. Review of accrual to past COG studies of new agents demonstrates the accrual of both genders and all NIH-identified ethnicities to such studies. Efforts will be made to extend the accrual to a representative population, but in a Phase 1 trial which will accrue a limited number of patients, a balance must be struck between patient safety considerations and limitations on the number of individuals exposed to potentially toxic or ineffective treatments on the one hand and the need to explore gender, racial, and ethnic aspects of clinical research on the other. If differences in outcome that correlate to gender, racial, or ethnic identity are noted, accrual may be expanded or additional studies may be performed to investigate those differences more fully.

11.5 Pharmacokinetic and Response Analysis

A descriptive analysis of pharmacokinetic (PK) parameters of MLN4924 (pevonedistat) will be performed to define systemic exposure, drug clearance, and other pharmacokinetic parameters. The PK parameters will be summarized with simple summary statistics, including means, medians, ranges, and standard deviations (if numbers and distribution permit).

While the primary aim of this study is to evaluate the toxicity of MLN4924 (pevonedistat), patients will have disease evaluations performed as indicated in [Section 8.1](#). Disease response will be assessed according to criteria for patients with AML, and will be reported descriptively.

All these analyses will be descriptive and exploratory and hypotheses generating in nature.

12.0 EVALUATION CRITERIA

12.1 Common Terminology Criteria for Adverse Events (CTCAE)

The descriptions and grading scales found in the revised NCI Common Terminology Criteria for Adverse Events (CTCAE) version 5.0 will be utilized for AE reporting. All appropriate treatment areas should have access to a copy of the CTCAE version 5.0. A copy of the CTCAE version 5.0 can be downloaded from the CTEP website (http://ctep.cancer.gov/protocolDevelopment/electronic_applications/ctc.htm).

12.2 Response Criteria for Patients with Leukemia

12.2.1 Complete Remission (CR)

Attainment of an M1 bone marrow (< 5% blasts and adequate marrow cellularity) with no evidence of circulating blasts or extramedullary disease and with recovery of peripheral blood counts (ANC \geq 1000/uL and platelet count \geq 100,000/uL). Flow cytometry may be useful to distinguish between leukemia and a regenerating bone marrow. There is no requirement for bone marrow cellularity.

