4.1 Inclusion Criteria

4.1.1 Age: Patients must be ≥ 1 months and ≤ 21 years of age at the time of study enrollment.

4.1.2 Diagnosis:

4.1.2.1 Patients must have had histologic verification of AML at the original diagnosis. Patients must have one of the following:

a) Recurrent disease in $\geq 1^{\text{st}}$ relapse with $\geq 5\%$ blasts in the bone marrow (M2/M3) marrow OR immunophenotypic evidence of disease with $\geq 0.1\%$ blasts detected by flow cytometry, OR evidence of recurrent cytogenetic or molecular abnormalities consistent with relapse, with or without extramedullary disease.

b) Refractory AML is defined as $\geq 5\%$ blasts in the bone marrow (M2/M3) after ≥ 2 induction attempts (i.e., 2 cycles of chemotherapy).

4.1.2.2 Patients with advanced MDS, including MDS that has progressed to AML, and have experienced relapse or are refractory after ≥ 1 course of induction therapy, are eligible.

4.1.3 Performance Level: Karnofsky $\geq 50\%$ for patients > 16 years of age and Lansky ≥ 50 for patients ≤ 16 years of age (See [Appendix I](#)).

4.1.4 Prior Therapy:

4.1.4.1 Patients must have fully recovered from the acute toxic effects of all prior anti-cancer therapy and must meet the following minimum duration from prior anti-cancer directed therapy prior to enrollment. If after the required timeframe, the numerical eligibility criteria are met, e.g., blood count criteria, the patient is considered to have recovered adequately.

a. Cytotoxic chemotherapy or other anti-cancer agents known to be myelosuppressive. See DVL homepage for commercial and Phase 1 investigational agent classifications. For agents not listed, the duration of this interval must be discussed with the study chair and the study-assigned Research Coordinator prior to enrollment.

• ≥ 14 days must have elapsed after the completion of other cytotoxic therapy, with the exception of hydroxyurea, for patients not receiving standard maintenance therapy. Additionally, patients must have recovered from all acute toxic effects of prior therapy.

NOTE: Cytoreduction with hydroxyurea must be discontinued ≥ 24 hours prior to the start of protocol therapy.

b. Anti-cancer agents not known to be myelosuppressive (e.g. not associated with reduced platelet or ANC counts): ≥ 7 days after the last dose of agent. See DVL homepage for commercial and Phase 1 investigational agent classifications. For agents not listed, the duration

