12.2.2 Complete Remission with Partial Recovery of Platelet Count (CRp)

Attainment of an M1 bone marrow (< 5% blasts) and no evidence of circulating blasts or extramedullary disease and with recovery of ANC \geq 1000/uL and platelet transfusion independence (defined as no platelet transfusions x 1 week).

12.2.3 Complete Remission with Incomplete Blood Count Recovery (CRi):

Attainment of an M1 bone marrow (<5% blasts) and no evidence of circulating blasts or extramedullary disease and with ANC $<$ 1000/uL or platelet count $<$ 100,000/uL without platelet transfusion independence (defined as no platelet transfusions x 1 week).

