12.2.4 Partial Response

Attainment of M2 marrow status (\geq 5% or $<$ 25% blasts cells and adequate cellularity) and at least 50% decrease in bone marrow blast percent from baseline. Bone marrow must have adequate cellularity (e.g. \geq 10% if a biopsy is performed) to determine response. PR status will not be included in the calculation of response to the regimen. A repeat bone marrow aspiration within 14 days may be required to distinguish between a PR and increased blasts caused by bone marrow regeneration, and is left to the discretion of the investigator.

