12.2.5 Treatment Failure

The definition of treatment failure includes:

- A. An increase in the extent of bone marrow infiltration by leukemic cells (absolute increase of \geq 20% blasts) OR
- B. Development of extramedullary disease (EMD) OR
- C. M2 marrow that does not qualify for PR status OR
- D. An M1 marrow with circulating blasts OR
- E. $>$ 25% blasts in the bone marrow after Cycle 1 of therapy
- F. Subjects who have persistent CNS disease despite 6 doses of IT cytarabine or IT triples

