12.2.6 Relapse

Morphologic relapse after CR/CRp/CRi is defined as a reappearance of leukemic blasts in the peripheral blood or $\geq 5\%$ blasts in the bone marrow not attributable to any other cause (e.g. bone marrow regeneration after therapy). In the setting of recent treatment, if there are no circulating blasts and the bone marrow contains 5-20% blasts, a repeat bone marrow performed at least a week later is necessary to distinguish relapse from bone marrow regeneration. Should flow cytometric or molecular analyses suggest relapse (by reappearance of similar immunophenotype or mutation to the original leukemia) in the presence of $< 5\%$ blasts or $\geq 5\%$ blasts in a regenerating marrow, a repeat bone marrow performed at least a week later is necessary to confirm relapse by morphologic methods. In such instances, the date of recurrence is defined as the first date that more than 5% blasts were observed in the bone marrow. The reappearance or development of cytogenetically proven extramedullary disease also indicates relapse. Molecular and/or genetic relapse is characterized by reappearance of a cytogenetic or molecular abnormality.

12.2.7 Unevaluable:

Aplastic or severely hypocellular marrow. In this instance, marrow evaluation should be repeated weekly until response determination can be made through at least Day 60.

12.2.8 Bone Marrow Classification:

- M1 is $< 5\%$ blasts
- M2 is 5-25% blasts
- M3 is $> 25\%$ blasts

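### Some low-burden entrants can already meet the written CR or CRp criteria before dosing, and no rule keeps them apart in the descriptive response rate

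*Combined protocol and SAP*

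**What the plan says.** **Entry.** Section 4.1.2.1(a) gives three alternative routes for relapsed AML. The first is at least 5% marrow blasts. The other two, after a floor of 0.1% for flow, read "blasts detected by flow cytometry, OR evidence of recurrent cytogenetic or molecular abnormalities consistent with relapse, with or without extramedullary disease". Refractory AML, section 4.1.2.1(b), does need at least 5%. Section 4.1.2.2 adds "Patients with advanced MDS, including MDS that has progressed to AML, and have experienced relapse or are refractory after" one or more induction courses, with no blast minimum. The marrow-function criterion in section 4.1.5.6 concerns hemoglobin only; there is no ANC or platelet limit.

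**Response.** CR (12.2.1) requires "Attainment of an M1 bone marrow (< 5% blasts and adequate marrow cellularity"), no circulating blasts or extramedullary disease, ANC of at least 1000/µL and platelets of at least 100,000/µL. CRp (12.2.2) requires "Attainment of an M1 bone marrow (< 5% blasts) and no evidence of circulating blasts or extramedullary disease", the same ANC, and platelet transfusion independence. CRi (12.2.3) has the same marrow, blood and extramedullary terms, with ANC below 1000/µL or platelets below 100,000/µL, followed by "without platelet transfusion independence (defined as no platelet transfusions x 1 week"). Only partial response (12.2.4) refers to baseline, and there the plan states "PR status will not be included in the calculation of response to the regimen".

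**Analysis.** Section 11.5 assesses response by AML criteria and reports it descriptively. Section 11.2 defines evaluability for adverse events but no response set. The unevaluable category (12.2.7) is limited to "Aplastic or severely hypocellular marrow".

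**The concern.** The entry criteria reach below 5% blasts, while the remission criteria start at that same 5% line and look only at the state after treatment. A patient enrolled as relapsed on flow or molecular evidence may therefore satisfy CR on the day of enrollment. None of the three remission categories asks for clearance of the abnormality that made the patient eligible.

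At stake is the sole secondary aim (1.2.1), the description of antitumor activity. If these patients are pooled, the rate mixes those who reached remission criteria with those who kept a status they already had. It is then hard to set beside rates in overt disease. A confidence interval does not show this problem, because it comes from the case definition and not from sampling.

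**Working it through.** **1. Who is affected.** Compare entry with the remission criteria:

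- Refractory AML: not affected, since at least 5% blasts are required.
- Under 5% marrow blasts, but circulating blasts or extramedullary disease at entry: not in CR at entry. Clearing that disease is a real response.
- Under 5% marrow blasts, blood and extramedullary sites clear, ANC at least 1000/µL, and platelets at least 100,000/µL or transfusion-independent: already meets CR or CRp as written.
- As the last group, but with ANC below 1000/µL: meets neither CR nor CRp. CRi depends on whether its platelet-transfusion qualifier applies to both count conditions or to the platelet condition only.

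**2. Can worsening read as remission?** Take a rise from 0.5% to 4% marrow blasts, with blood, extramedullary sites and counts unchanged. The first failure item in section 12.2.5, "An increase in the extent of bone marrow infiltration by leukemic cells", needs an absolute rise of at least 20% blasts. The others need new extramedullary disease, an M2 marrow short of PR, circulating blasts, more than 25% blasts, or persistent CNS disease. None is met, and the patient still satisfies CR or CRp.

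**3. The plan's own figures.** The documents state no response rate or response sample size. Section 11.1's enrollment totals reproduce as (2 × 6 + 6)/0.8 = 22.5, rounded up to 23, and (2 × 12 + 6)/0.8 = 37.5, rounded up to 38. I therefore use n = 18 and n = 30. I also use n = 12, the case where Dose Level 1 is accepted on 6 patients and 6 PK patients follow.

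**4. Size if pooled.** Let f be the share of patients who meet CR or CRp at entry, counts included (CRi on the wider reading). Let q be the share of them classed CR/CRp/CRi after treatment, and p the rate in all others. Then

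pooled rate = (1 − f)p + fq, so shift = f(q − p).

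All three inputs are assumptions. I take f = 10–30% and q = 80–100%. For p I borrow background rates: 59% and 69% (section 2.1, pediatric Flu/AraC without and with daunoXome) and 39% (section 2.3.1, older adults on azacitidine plus pevonedistat).

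| p | q | f = 10% | f = 20% | f = 30% |
|---|---|---|---|---|
| 59% | 80% | +2.1 | +4.2 | +6.3 |
| 59% | 100% | +4.1 | +8.2 | +12.3 |
| 59% | 50% | −0.9 | −1.8 | −2.7 |
| 69% | 80% | +1.1 | +2.2 | +3.3 |
| 69% | 100% | +3.1 | +6.2 | +9.3 |
| 39% | 80% | +4.1 | +8.2 | +12.3 |
| 39% | 100% | +6.1 | +12.2 | +18.3 |

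Shifts are in percentage points. The shift is zero if f = 0 or q = p.

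**5. Scale.** Standard error at p = 59%, √(0.59 × 0.41/n): 14.2 points at n = 12, 11.6 at n = 18, 9.0 at n = 30. At n = 18 the shift for p = 59% passes one standard error only when q = 100% and f exceeds 0.116/0.41 = 28%. At n = 12 it never does within the range. With p = 39% the standard error at n = 18 is √(0.39 × 0.61/18) = 11.5 points, and the upper half of that range exceeds it.

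**6. Whole-number example (assumed).** Fourteen other patients with 8 remissions give 57.1%. Adding four who met the criteria at entry gives 12/18 = 66.7% if all four still meet them, 11/18 = 61.1% if three do, and 10/18 = 55.6% if two do. The exact 95% interval for 11/18 is 35.7% to 82.7%.

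**The case against.** The strongest reply is that the definitions already imply a change. CR speaks of attaining an M1 marrow and of recovery of counts, and a patient with both at entry has attained and recovered nothing. Section 12.2.1 also lets flow cytometry help to tell leukemia from regeneration. This reading is possible, but no rule states it and the flow remark is discretionary. If it is the intended reading, these patients have no remission category and no stated place in the denominator, so a sentence is still needed.

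Second, response is descriptive and exploratory, with no target rate, test or decision rule, and a baseline split could be tabulated at reporting from data already collected. This stands and limits the importance of the point. Writing the split down beforehand still avoids choosing the denominator after the responses are known.

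Third, nothing shows that such patients will enroll. Appendix VI-A withholds one sample type when minimal residual disease is below 1%, which suggests that low-burden patients were foreseen, but the note may also concern end-of-cycle samples.

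Fourth, not every low-burden entrant qualifies. Those neutropenic at entry do not meet CR or CRp, and later count recovery in them is a genuine change. This also stands, and both the definition of f and the fix allow for it.

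**Conclusion.** The overlap between entry and remission criteria is in the text. Applied as written, the rule can class unchanged or rising disease below 5% blasts as remission. This is a minor-to-moderate correction to a descriptive secondary aim.

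A reader might infer that the trial's response rate will be inflated. The documents do not support that. No text says these patients will be pooled, none may enroll, and the shift is negative when q is below p. Its size and sign are unknown because f, q and p are all assumed, and the borrowed values of p come from other regimens. At p = 59% or 69% most illustrative shifts lie within one standard error; a lower p makes them larger. A reader might also infer that dose confirmation is compromised. It is not: the RP2D rests on DLTs, and neither it nor the sample size uses response.

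**What to change.** Amend sections 11.5 and 12.2 as follows.

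1. Report the CR/CRp/CRi rate, with its denominator stated, in patients who at baseline have at least 5% marrow blasts, circulating blasts or extramedullary disease. Apply this to the AML and MDS routes alike.
2. List the remaining low-burden entrants separately and leave them out of that rate. Show their baseline and post-treatment marrow blasts and blood counts, so that count recovery in those cytopenic at entry is visible. Where tested, also show clearance of the qualifying flow, cytogenetic or molecular abnormality.

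The cost is wording only. The split uses the pre-study marrow, CBC with differential, physical exam and CSF that section 8.1 already requires. The denominator may be slightly smaller and the stated rate possibly lower, and the separate list may hold few or no patients. Clearance data will be incomplete, because section 8.1 mandates no end-of-cycle flow, cytogenetic or molecular test.

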12.2.2 Complete Remission with Partial Recovery of Platelet Count (CRp)

Attainment of an M1 bone marrow (< 5% blasts) and no evidence of circulating blasts or extramedullary disease and with recovery of ANC \geq 1000/uL and platelet transfusion independence (defined as no platelet transfusions x 1 week).

12.2.3 Complete Remission with Incomplete Blood Count Recovery (CRi):

Attainment of an M1 bone marrow (<5% blasts) and no evidence of circulating blasts or extramedullary disease and with ANC $<$ 1000/uL or platelet count $<$ 100,000/uL without platelet transfusion independence (defined as no platelet transfusions x 1 week).

12.2.4 Partial Response

Attainment of M2 marrow status (\geq 5% or $<$ 25% blasts cells and adequate cellularity) and at least 50% decrease in bone marrow blast percent from baseline. Bone marrow must have adequate cellularity (e.g. \geq 10% if a biopsy is performed) to determine response. PR status will not be included in the calculation of response to the regimen. A repeat bone marrow aspiration within 14 days may be required to distinguish between a PR and increased blasts caused by bone marrow regeneration, and is left to the discretion of the investigator.

12.2.5 Treatment Failure

The definition of treatment failure includes:

- A. An increase in the extent of bone marrow infiltration by leukemic cells (absolute increase of \geq 20% blasts) OR
- B. Development of extramedullary disease (EMD) OR
- C. M2 marrow that does not qualify for PR status OR
- D. An M1 marrow with circulating blasts OR
- E. $>$ 25% blasts in the bone marrow after Cycle 1 of therapy
- F. Subjects who have persistent CNS disease despite 6 doses of IT cytarabine or IT triples

